The facilities that will be used for the study will be UK Chandler hospital, UK Polk Dalton clinic, UK Good Samaritan hospital, UK Good Samaritan ultrasound unit, UK Good Samaritan Radiology unit and UK laboratories. The blood and urine samples will be de-identified and stored in [name] lab at the University of Kentucky. The participants will continue to receive prenatal care as per their standard prenatal care from their obstetricians. If any medical concerns are addressed they will be immediately be referred back to their obstetrician.

Potential Risks & Benefits

Risks

- Describe any potential risks – including physical, psychological, social, legal, ability to re-identify subjects, or other risks. Assess the seriousness and likelihood of each risk.
- Which risks may affect a subject's willingness to participate in the study?
- Describe likely adverse effects of drugs, biologics, devices or procedures participants may encounter while in the study.
- *Qualitative research* - describe ethical issues that could arise while conducting research in the field and strategies you may use to handle those situations.
- Describe any steps to mitigate these risks.

Benefits

- Describe potential direct benefits to study participants – including diagnostic or therapeutic, physical, psychological or emotional, learning benefits. This cannot include incentives or payments.
- State if there are no direct benefits.
- Describe potential benefits to society and/or general knowledge to be gained.

Describe why potential benefits are reasonable in relation to potential risks. If applicable, justify why risks to vulnerable subjects are reasonable to potential benefits.

The most common side effects seen with aspirin use are but not limited to nausea, vomiting, heartburn in the mother seen in about 10% of the patients. There is no increased risk for bleeding during antepartum, intrapartum or postpartum period and there are no known fetal risks with low dose aspirin. There is no risk to the control group involving low risk pregnant women as they do not meet criteria to receive aspirin during the study or outside of it.

The ultrasound assessments of the uterine and brachial arteries are non-invasive and do not pose any maternal or fetal risks. Patients may experience discomfort using ultrasound assessment of the brachial artery which involves inflating the blood cuff around the forearm for 5 minutes.

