The technique to measure flow mediated dilation has been validated and used extensively in research involving pregnant women. Patients may experience discomfort at the time of cuff inflation in their forearm for 5 minutes. We will continue to monitor patients during their hospitalizations and monitor for an increase between groups in adverse maternal and neonatal outcomes as defined as placental abruption, postpartum hemorrhage, epidural or spinal hematoma, fetal intracranial hemorrhages, premature closure of ductus or maternal deaths. PI will implement these monitoring procedures and data will be reviewed at 6- month intervals to determine if a significant increase in adverse events is noted between groups.

2. Assuring compliance with the requirements regarding the reporting of unanticipated problems or adverse experiences:

The PI will review the collected data at regular intervals to determine if adverse maternal or neonatal events are potentially related to the exposure. If a root cause analysis suggests that the adverse or unanticipated outcome is due to patient's participation in this research, then a severe adverse event will promptly be reported to IRB. The patient will also be notified and aspirin dosing will be changes as needed.

3. Any action resulting in a temporary or permanent suspension of the study is reported to the IRB promptly. This would include but not limited to a increase in serious maternal and neonatal adverse events as defined above

4. Assuring data accuracy and protocol compliance The PI will monitor data accuracy and protocol compliance

5. Assuring communication among multi-center sites adequately protects the participant (if this is a multi-center study in which the lead PI or UK is the coordinating institution) - Not applicable

[Back to Top](#)

Future Use and Sharing of Material (e.g., Data/Specimens/Information)

If the material collected for this study will be used by members of the research team or shared with other researchers for future studies, please address the following:

- list the biological specimens and/or information that will be kept
- briefly describe the types, categories and/or purposes of the future research
- describe any risks of the additional use
- describe privacy/confidentiality protections that will be put into place

- describe the period of time specimens/information may be used
- describe procedures for sharing specimens/information with secondary researchers

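### A single safety event goes to the IRB only if a root cause analysis points to study participation, a stricter test than the plan's own review question

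*Combined protocol and SAP*

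**What the plan says.** Three items of the protocol's Data and Safety Monitoring section matter here.

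- **Item 1** names the outcomes to be watched: "placental abruption, postpartum hemorrhage, epidural or spinal hematoma, fetal intracranial hemorrhages, premature closure of ductus or maternal deaths". The PI runs this monitoring, and "data will be reviewed at 6- month intervals to determine if a significant increase in adverse events is noted between groups".
- **Item 2** deals with reporting. The PI looks at the data at regular intervals "to determine if adverse maternal or neonatal events are potentially related to the exposure". The next sentence sets the reporting rule. Its condition is: "If a root cause analysis suggests that the adverse or unanticipated outcome is due to patient's participation in this research". The consequence, where that condition is met, is: "then a severe adverse event will promptly be reported to IRB". Telling the patient comes straight after, in the same sequence.
- **Item 3** is a separate route: "Any action resulting in a temporary or permanent suspension of the study is reported to the IRB promptly". It counts an increase in the serious events of item 1 among the cases it covers.

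The Study Design section describes an open-label comparison of 81 mg and 162 mg. The SAP contains no comparison of adverse events, so it adds no rule or threshold.

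**The concern.** Item 2 asks one question and acts on another. The review asks whether an event could be related to aspirin. The report depends on an analysis suggesting that the event was caused by taking part. An event can pass the first test and fail the second, and the plan does not say what then happens to it.

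This matters because several listed outcomes, for example abruption and postpartum hemorrhage, can occur for reasons other than aspirin, and the randomised women are enrolled because they are at high risk. Examining one case will often leave the cause open. A dose effect on such outcomes would show as an excess across cases, which no single root cause analysis can reveal. At stake is whether the IRB, the only body outside the study team that this section names, hears promptly of events that the team itself regards as possibly related to the drug.

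**Working it through.** The documents give no figure to reproduce on this point: no event rate, alpha, power or threshold for safety. The main check is therefore textual.

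**Step 1. Follow an event through item 2.**

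| PI's review | Root cause analysis | Single-event report to the IRB |
|---|---|---|
| Not potentially related | – | None |
| Potentially related | Suggests due to participation | Prompt |
| Potentially related | Does not suggest this | No route stated |
| Potentially related | Pending or not done | No route stated until it is complete |

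The third and fourth rows are the gap. The fourth is open-ended, because the item sets no time limit for the analysis. It also does not say who performs it or which events receive one, and it does not define what makes an event severe.

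**Step 2. Can item 3 carry those events?** Item 3 needs no causal finding for the individual case, and item 1's six-monthly review between groups feeds it. It is, however, tied to suspension of the study. It acts on an increase, not on one event, and the size of increase is not given.

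**Step 3. How sensitive could the group-level review be?** Inputs: 100 women per aspirin arm, from the study population text above the Participant Demographics table. Assumptions not in the documents: the word significant in item 1 means a two-sided test at 0.05; the rate in the 81 mg arm is 1 to 10%; the rate in the 162 mg arm is double. With p̄ the mean of the two rates and n the number per arm, the normal-approximation power is

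Φ{ [ (p2 − p1) − 1.96·√(2p̄(1−p̄)/n) ] / √[ (p1(1−p1) + p2(1−p2))/n ] }.

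For 3% against 6% with n = 100:

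- √(2 × 0.045 × 0.955/100) = 0.0293
- √[(0.0291 + 0.0564)/100] = 0.0292
- (0.03 − 1.96 × 0.0293)/0.0292 = −0.94, and Φ(−0.94) = 0.17

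| Rates, 81 mg vs 162 mg | Normal approximation | Fisher's exact test |
|---|---|---|
| 1% vs 2% | 8% | 1% |
| 3% vs 6% | 17% | 9% |
| 5% vs 10% | 27% | 19% |
| 10% vs 20% | 51% | 44% |

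Earlier reviews see fewer women. Over the same rates, power is 6 to 29% with 50 per arm (Fisher 0 to 20%) and 5 to 16% with 25 per arm (Fisher 0 to 9%). These are single-look figures; repeated looks would raise the cumulative chance of a flag, including a false one. The Project Information section caps subjects at 209, whereas the study population text plans about 250. With the same allocation, 209 × 100/250 ≈ 84 per arm, and power would be lower than in the table.

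**The case against.** The strongest reply is that items 1 and 3 exist to catch what a single case cannot show. They compare groups, need no case-level causality, and reach the IRB when the listed serious events increase. This stands in part. A reader might infer that the IRB sees nothing until causation has been established; the documents do not support that, because item 3 is a second route. It does not close the gap for single events, for the reasons in steps 2 and 3 of the working.

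Second, the wording is softer than it may first appear. The analysis need only suggest a link, and the text does not assign it to the PI, although the PI carries out the review just before. Both points stand. Even so, an analysis suggesting that an event was caused by participation is a higher bar than a possible relation.

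Third, item 2's heading refers to reporting requirements, which may be set out elsewhere. The pages after the Signatures (Assurances) heading are not in the text, so broader duties may exist. This stands as a limit on the finding.

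Fourth, a reader might see a contradiction between the Potential Risks & Benefits section ("There is no increased risk for bleeding during antepartum, intrapartum or postpartum period") and the monitoring of bleeding outcomes. There is none: a plan can monitor for a risk that it believes absent. Nor does anything make that sentence the standard for judging causality, so how a particular hemorrhage would be classified cannot be predicted from it.

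Last, aspirin is planned to stop at 36 weeks, so some delivery-related events will follow the end of dosing. An unknown share of listed events might reasonably be judged unrelated under either test.

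**Conclusion.** The point holds as a mismatch within item 2. The rule for reporting a single event is stricter than the review question it follows, and on the visible text an event that falls between the two has no single-event route to the IRB. Item 3 is a real but weak second route: group-level, tied to suspension and without a threshold.

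The number of events affected cannot be derived, because the documents give no rates and do not show how often a root cause analysis would point to participation. A reader might infer that almost no hemorrhages would be reported; nothing in the documents supports a figure of that kind. The power figures are only illustrative. They show that, on the assumptions stated in the working, a group comparison would often miss a doubling, so it should not be relied on to replace reporting of individual events. The conclusion about item 2 does not depend on them. It does depend on there being no wider reporting duty in the pages not available.

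**What to change.** Align item 2's trigger with its own review question. Any event on the item 1 list that is judged potentially related to aspirin should be reported promptly to the IRB, without waiting for the root cause analysis, whose result can follow. The remaining listed events should go into a listing by arm, drawn from the existing six-monthly review and supplied to the IRB at continuing review. The same edit should say who makes the relatedness judgement and what counts as severe.

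The change concerns reporting only and takes no position on item 2's clause about dosing. It costs a short IRB modification, the work of preparing the listing, and a modest number of extra reports, some of them background events. If the assurance pages already impose the wider duty, a cross-reference from item 2 and agreement in wording would be enough for single-event reporting.

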Inserted	1031173	104560	10446600	SP	N	[name]	[contact]						N	Data Analysis/Processing		P	N	ash231	4/28/2025 10:06:22 AM	N			

Modification Comment by [name] - ORI to PI on 4/28/2025 10:13:11 AM
Please add the changes being made to "[name]" - highlighted in study personnel section but not included here.

Statistical Analysis Plan NCT03893630 6/27/2025

To begin, continuous variables (age, BMI, gestational age at delivery, etc.) will be summarized with descriptive statistics (n, mean, standard error); categorical variables (e.g., pre-eclampsia, method of conception, etc.) will be summarized with counts and percentages.

The primary outcome, difference in uterine artery pulsatility index (PI) will be calculated as the difference in PI for each patient between each trimester visit. PI at each visit will be calculated by averaging left-side and right-side PIs from each of three (or all available) images on each side for each patient using ultrasound technology. For a very limited number of images identified using clinical expertise, the MATLAB code below will be used to produce PI values if ultrasound technology is insufficient.

An independent and automated image analysis pipeline will be developed using R to crop images and MATLAB to perform image analysis. For each available ultrasound image, an estimated mean PI will be calculated as the average of the PI from each analyzable waveform. For each patient at each visit, left- and right-side estimates will be obtained using the median of the available image-level estimates, since the median is more robust to outliers resulting from images that might be difficult to read. Finally, the mean PI for each patient at each visit will be calculated using the average of the left- and right-side estimates. Means and SDs of these indices will be compared to (1) ensure that there are no drastic differences from the values calculated using the ultrasound technology and the alternative pipeline, and (2) demonstrate the robustness of the calculated primary outcome values.

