□ 7) Research on individual or group characteristics or behavior (including, but not limited to, research on perception, cognition, motivation, identity, language, communication, cultural beliefs or practices, and social behavior) or research employing survey, interview, oral history, focus group, program evaluation, human factors evaluation, or quality assurance methodologies. (Note: Some research in this category may be exempt from the HHS regulations for the protection of human subjects. This listing refers only to research that is not exempt.)

MODIFICATION REQUEST SECTION

0 unresolved
comment(s)

*** If this modification changes the scope of your activities to include COVID-19 related research, please insert "COVID19" at the start of your Project and Short Titles.***

Select One:

- This modification does not increase risk to study participants.
- This modification may or will increase risk to study participants.

Is this modification request due to an Unanticipated Problem/Adverse Event, or Protocol Violation?

- Yes
- No

In your professional opinion, does this modification involve information that might relate to a subject's willingness to continue to take part in the research?

- Yes
- No

If yes, state how the information will be communicated to subjects (i.e., re-consent, send letter, etc.):

For each proposed modification, include a justification.

Example: [name], is being added as co-investigator because she has expertise with the subjects on this protocol. She has completed human subject protections training, and is authorized to obtain consent.

[name] , [name] and [name] are being added as project assistance for data analysis because they have expertise with the subjects on this protocol.

PROJECT INFORMATION**0 unresolved comment(s)**

Title of Project: (Use the exact title listed in the grant/contract application, if applicable).

If your research investigates any aspect of COVID-19, please include "COVID19" at the beginning of your Project Title and Short Title

Role of aspirin in maternal endothelial dysfunction and uterine artery blood flow in women at risk for preeclampsia

Short Title Description

Please use a few key words to easily identify your study - this text will be displayed in the Dashboard listing for your study.

ASPERIN Trial

Anticipated Ending Date of Research Project: 3/31/2026

Maximum number of human subjects (or records/specimens to be reviewed) 209

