The study population will include pregnant women between the ages 18 and 45 years enrolled as cases and controls. Women at high risk for preeclampsia will be enrolled as cases and those without risk factors for preeclampsia will be approached to serve as a control population. Approximately 250 eligible women will be enrolled in this study (50 in the normal control arm, 100 in the low dose 81 mg per day arm, and 100 in the 162 mg per day arm). Eligible patients will be recruited from UK clinics and the UK Good Samaritan ultrasound unit at the time of their scheduled prenatal visits or ultrasound appointments. Women who plan to deliver at University of Kentucky Chandler Hospital will be approached for enrollment.

The risk factor assessment to screen women at high risk for preeclampsia include:

1. History of preterm preeclampsia, especially when accompanied by an adverse outcome
2. Chronic hypertension
3. Type 1 and Type 2 diabetes
4. Renal diseases
5. Autoimmune disease

Exclusion criteria include:

1. Pregnant women younger than 18 years or older than 45 years
2. Multiple gestations
3. History of allergy (urticaria or anaphylaxis) to aspirin or aspirin related products asthma that worsens after aspirin use
4. Patients with gastrointestinal or genitourinary bleeding
5. Patients with peptic ulcer disease
6. Patients with severe liver dysfunction
7. Patients who have undergone bypass surgery
8. Patients on anticoagulant medication(s)
9. Women with anomalous fetus

Recruitment and data collection is expected to last throughout 2018-2022 academic years. Data analysis is expected to be accomplished during 2019-2022 academic years.

Attachments

Indicate the targeted/planned enrollment of the following members of minority groups and their subpopulations. Possible demographic sources: [Census Regional Analyst Edition](#), [Kentucky Race/Ethnic Table](#), [Kentucky Population Data](#).

(Please note: The IRB will expect this information to be reported at Continuation Review time for Pre-2019 FDA-regulated Expedited review and Full review applications):

Participant Demographics

	Cisgender Man 	Cisgender Woman 	TGNB/TGE 	Unknown/Not Reported
American Indian/Alaskan Native:	0	2		
Asian:	0	10		
Black/African American:	0	35		
Latinx:	0	25		
Native Hawaiian/Pacific Islander:	0	2		
White:	0	166		
American Arab/Middle Eastern/North African:		1		
Indigenous People Around		1		

the World: _____

More than One Race:	8		
Unknown or Not Reported:	0	0	

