This is a single center, prospective, randomized, open-label clinical trial. The experimental group will include pregnant women who are identified at high risk for preeclampsia either by history, presence of risk factors, or abnormal uterine artery Doppler impedance. They will be divided into two groups based on their body mass index (BMI) (<30 and =30). Patients in each group will be randomized to receive either aspirin 81 mg (1 tablet of baby aspirin) or aspirin 162 mg (2 tablets of baby aspirin) daily initiated between 11 and 16 weeks of gestation and continued until 36 weeks of gestation. There will be a third control group of pregnant women at low risk for preeclampsia based on their risk factor assessment to provide baseline data. The control group will not receive aspirin. Both of the experimental and control groups will be assessed with uterine artery Doppler studies and FMD of the brachial artery at three different time points in pregnancy: at enrollment between 11 and 16 weeks, between 18 and 22 weeks (+/- 7 days), and between 28 and 32 weeks of gestation(+/- 7 days). We will obtain baseline blood and urine samples at the time of enrollment and later between 28 and 32 weeks (+/- 7 days) to assess salicylate levels, thromboxane and endothelin-1 levels. We will also obtain cord blood and placental samples from the experimental and control population at the time of delivery.

Attachments

Subject Recruitment Methods & Advertising

Describe how the study team will identify and recruit subjects. Please consider the following items and provide additional information as needed so that the IRB can follow each step of the recruitment process.

- How will the study team identify potential participants?
- Who will first contact the potential subjects, and how?
- Will you use advertisements? If so, how will you distribute those?
- How and where will the research team meet with potential participants?
- If applicable, describe proposed outreach programs for recruiting women, minorities, or disparate populations.
- How you will minimize undue influence in recruitment?
- Attach copies of all recruiting and advertising materials (emails, verbal scripts, flyers, posts, messages, etc.).

For additional information on recruiting and advertising:

- [IRB Application Instructions - Advertisements](#)
- [PI Guide to Identification and Recruitment of Human Subjects for Research](#)

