The research procedures including patient enrollment will happen at the time of their routine prenatal visits and no additional visits for the purpose of this research are anticipated. The procedures patients will undergo during their visits and the timeline are shown in the attached table. The experimental group will include pregnant women who are identified at high risk for preeclampsia either by history, presence of risk factors, or abnormal uterine artery Doppler impedance. They will be divided into two groups based on their body mass index (BMI) (<30 and >=30). Patients in each group will be randomized to receive either aspirin 81 mg (1 tablet of baby aspirin) or aspirin 162 mg (2 tablets of baby aspirin) daily initiated between 11 and 16 weeks of gestation and continued until 36 weeks of gestation. There will be a third control group of pregnant women at low risk for preeclampsia based on their risk factor assessment to provide baseline data. The control group will not receive any aspirin.

After their initial enrollment, patients in the experimental group will be divided into 2 groups based on their body mass index (BMI) : <30 and >=30. Patients in each group will be randomized to receive aspirin 81 mg(1 low-dose aspirin tablet) or aspirin 162 mg (2 low dose aspirin tablets per day) daily until 36 weeks of gestation. Prescribing low dose aspirin is part of the standard prenatal care for women who are identified as at high risk for preeclampsia.

The prescription for aspirin for the patients enrolled in the study will be sent to the UK Good Samaritan Hospital outpatient pharmacy. When patients are randomized to Aspirin 162 mg (2 tablets of baby aspirin) and there is an additional cost to the patient due to the higher dose. The Division of Maternal Fetal Medicine at UK will receive a monthly statement from UK Good Samaritan Hospital pharmacy for every dose of 162mg that was filled during the previous month.

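### The SAP defines the primary outcome as a raw change in PI and names no baseline covariate; adding enrolment PI to the dose comparison would recover precision at no data cost

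*Combined protocol and SAP*

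**What the plan says.** The primary outcome paragraph of the SAP states: "The primary outcome, difference in uterine artery pulsatility index (PI) will be calculated as the difference in PI for each patient", taken from one trimester's visit to another. The value for a single visit is obtained by "averaging left-side and right-side PIs from each of three (or all available) images on each side". The rest of the SAP covers descriptive summaries and a cross-check of the ultrasound values against an automated image pipeline. It names no between-arm test, model, covariate or stratification term, and does not say which of the possible visit-to-visit differences decides the trial.

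The protocol's Study Design section schedules uterine artery Doppler "at three different time points in pregnancy: at enrollment between 11 and 16 weeks" and at two later visits, so a pre-treatment PI is planned for every woman. Randomisation is within BMI groups (below 30, and 30 or above), according to Research Procedures: "Patients in each group will be randomized to receive either aspirin 81 mg (1 tablet of baby aspirin) or aspirin 162 mg". The study population description plans "100 in the low dose 81 mg per day arm, and 100 in the 162 mg per day arm", plus 50 low-risk controls who are not randomised.

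**The concern.** A comparison of mean changes with no baseline term fixes the coefficient of enrolment PI at 1. The slope that minimises variance is r times the ratio of follow-up SD to enrolment SD. When that slope is below 1, subtracting the whole of the enrolment value removes too much and leaves noise in the contrast that a covariate would take out.

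The 162 mg against 81 mg contrast is the trial's question. An unadjusted comparison would give it a wider confidence interval, and lower power, than the same scans can support.

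**Working it through.** **The plan's own figures.** The only one available is enrolment: 50 + 100 + 100 = 250. No alpha, power, effect size, PI SD, correlation or dropout rate is given, so there is no sample-size calculation to reproduce.

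**Inputs.** 100 women per randomised arm (study population description). Assumed: two-sided alpha 0.05, 80% power, no dropout, and a range for r and for k = follow-up SD / enrolment SD.

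**Formulas.** Let s0 and s1 be the SDs of PI at enrolment and follow-up, and b = r × s1/s0. Per-woman variance behind the dose contrast:

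- raw change: s0² + s1² − 2·r·s0·s1
- adjusted for enrolment PI: s1²(1 − r²)
- difference between the two: s0²(1 − b)², which is never negative and is zero only at b = 1.

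With equal SDs (k = 1, variances in units of the PI variance) these become 2(1 − r) and 1 − r². Their ratio is (1 + r)/2, so adjustment saves (1 − r)/2.

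| r | raw change | adjusted | ratio | variance saved | power if raw change has 80% |
|---|---|---|---|---|---|
| 0.3 | 1.40 | 0.91 | 0.65 | 35% | 93.5% |
| 0.5 | 1.00 | 0.75 | 0.75 | 25% | 89.9% |
| 0.7 | 0.60 | 0.51 | 0.85 | 15% | 86.0% |
| 0.9 | 0.20 | 0.19 | 0.95 | 5% | 82.0% |

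So 65, 75, 85 and 95 women per arm with adjustment match 100 per arm without it. A simulation with 100 per arm (4,000 runs) gave ratios of 0.653, 0.744 and 0.857 at r = 0.3, 0.5 and 0.7, in line with the formula.

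**Detectable difference.** (1.96 + 0.842) × √(2/100) = 0.396 SD units. At r = 0.5 and k = 1 this gives 0.396 × √1.00 = 0.40 for raw change and 0.396 × √0.75 = 0.34 adjusted.

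**Unequal SDs.** If the SD falls with gestation, the gain grows. At k = 0.75 and r = 0.5, raw change is 1 + 0.5625 − 0.75 = 0.8125 and adjusted is 0.5625 × 0.75 = 0.422, a ratio of 0.52. Over r = 0.3 to 0.9 at this k, the ratio runs from 0.46 to 0.56. If the SD rises, the gain can vanish. At k = 1.25 and r = 0.8, b = 1: raw change is 1 + 1.5625 − 2 = 0.5625 and adjusted is 1.5625 × 0.36 = 0.5625.

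**The outcome can stay as it is.** Regressing (follow-up − enrolment) on dose and enrolment PI only moves the enrolment coefficient from b to b − 1. The dose estimate, the residuals and the standard error are identical to those from regressing follow-up PI on the same terms.

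**The case against.** The strongest reply is that the SAP does not refuse adjustment, because it specifies no dose comparison at all. That stands. A reader might infer a decision to analyse unadjusted, but the text supports only silence, with an unadjusted comparison of mean changes as the natural default. The absence of any between-arm model is the larger gap, and this point says what the model should contain.

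Four other readings go too far.

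- A reader might infer that a change score carries the whole of the baseline noise. With equal SDs that is true only at r = 0. Above r = 0.5 the change score is less noisy than follow-up PI alone (0.60 against 1.00 at r = 0.7).
- A reader might blame the outcome definition, and say that a null result could come from it. The equivalence shown above rules that out: the loss comes from leaving out the covariate.
- A reader might treat chance imbalance in enrolment PI as a separate bias. Under randomisation the change score is unbiased, and chance imbalance is already in its standard error. It is the same loss of precision, counted once.
- A reader might take the largest gains as established. No SD or correlation is given. The saving is small at high r, and averaging several images per side may raise r.

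The third-minus-second-visit difference contains no enrolment value, so the argument does not apply directly to it.

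**Conclusion.** The point holds as a matter of precision. On the default reading, the dose contrast carries baseline noise that a scheduled measurement could remove. With equal SDs the avoidable share of the variance is (1 − r)/2, or 35% down to 5% for r from 0.3 to 0.9. It is larger if PI SD falls with gestation, and smaller or nil as the slope of follow-up on enrolment PI nears 1. Asymptotically, adjustment is never less precise.

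The ratios do not depend on arm size, but the detectable differences do. They use 100 per arm, whereas the Project Information section gives "Maximum number of human subjects (or records/specimens to be reviewed) 209". Scaled pro rata (an assumption), that is 209 × 100/250 ≈ 84 per arm, and the detectable differences at r = 0.5 and k = 1 become 0.43 and 0.37. The conclusion is unchanged. Validity of the randomised comparison is not in question.

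**What to change.** Keep change in PI from enrolment as the primary outcome. Add to the SAP that the 162 mg against 81 mg contrast, in the two randomised arms only and at one named follow-up visit, is estimated from a linear model with enrolment (11–16 week) PI and the BMI randomisation stratum (below 30, 30 or above) as covariates. Report the dose difference with its confidence interval. A log scale is optional and is not needed for this gain.

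If the second visit is the one named, its window must be reconciled between Study Design (18–22 weeks) and Research Procedures (20–22 weeks).

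Cost: one sentence and two model terms, with no new data.
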